(5 experimental, 6 control) and 3 incomplete subjects (2 experimental, 1 control). Differences between ZA-treated subjects and controls were 3% for the lumbar spine ($p < .05$); 12% for the total hip ($p < .05$), 5% for the femoral neck (NS), and 11% ($p < .05$) at the greater trochanter 12 months after study drug administration. In the ZA group, BMD at the total hip and greater trochanter were maintained from baseline, but the area of the femoral neck still lost 10% of the original BMD. In both of the above studies, pharmacologic intervention did not occur until 2-3 months post injury, when a notable amount of bone mass is already lost. Furthermore, neither study evaluated BMD at the distal femur and proximal tibia, two high risk areas for sublesional fractures after SCI.

Areal Bone Mineral Density

Since marked sub-lesional bone loss after SCI is found consistently^{5,6}, our study will provide new information on the effectiveness of ZA in preventing bone loss after SCI because it differs from prior studies in the following important aspects:

1. We will administer ZA within 21 days of SCI, when bone resorption is just beginning. This is sooner than the prior studies on ZA in SCI.
2. We will limit enrollment to patients with complete injuries, minimizing potential confounding between ambulatory and non-ambulatory subjects.
3. We will monitor calcium and vitamin D levels periodically throughout the study, with aggressive supplementation of all patients noted to be low, **and** we will supply supplemental calcium and vitamin D to all subjects to prevent anticipated losses in the initial year of injury³⁵.
4. We will evaluate the effect of ZA on BMD at the hip, the distal femur, and proximal tibia.

D. Study Design

This will be a prospective, double-blind, randomized, placebo-controlled trial with a 2:1 ratio of ZA to placebo in 48 persons with complete traumatic SCI.

Study Location and SCI Population

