This study will be conducted at the Regional Spinal Cord Injury Center of the Delaware Valley (RSCICDV), located at Thomas Jefferson University and Hospital (TJU/H) in Philadelphia, PA. TJUH, in affiliation with the Magee Rehabilitation Hospital, is designated as one of the United States' 16 Model Spinal Cord Injury Centers, by the National Institute on Disability and Rehabilitation Research, Department of Education's Office of Special Education and Rehabilitative Services. It is the only such facility in the Delaware Valley. The RSCIC has treated more than 3,000 persons with spinal cord injury and provides for multidisciplinary coordination of emergency and acute medical/surgical care, rehabilitation at the onset of acute care, with vocational evaluation and training, and lifetime follow-up care for persons with SCI. Over 50 percent of the SCI patient population is admitted to the RSCIC within three days of injury and the RSCIC has demonstrated a mortality rate of 5 percent. Over the past 5 years the RSCIC has annually admitted an average of 28-30 patients with complete SCI within 7 days of injury.

D.1. Subjects

Forty-eight subjects evaluated to have ASIA impairment scale Grade A injuries (motor and sensory complete) will be identified, screened, and approached to participate in the study. Persons who have recently experienced traumatic complete SCI and are within 21 days of injury are eligible to participate. The sample size calculation allows for reduced enrollment rates and drop outs. The ASIA impairment scale is detailed in **Table 3** below.

Table 3: ASIA Impairment Scale (ISNCSCI, 2011)

SCI Injury Grade	Description
A = Complete	No motor or sensory function is preserved in the sacral segments S4-S5.
B = Incomplete	Sensory but not motor function is preserved below the neurological level and includes the sacral segments S4-S5.
C = Incomplete	Motor function is preserved below the neurological level, and more than half of key muscles below the neurological level have a muscle grade less than 3.
D = Incomplete:	Motor function is preserved below the neurological level, and at least half of key muscles below the neurological level have a muscle grade of 3 or more.
E = Normal	Motor and sensory functions are normal.

D.2. Inclusion/Exclusion Criteria

Inclusion criteria:

- Ages 18- 65, male or female
- Traumatic SCI with Neurological level C4-T10, AIS A, Serum calcium level >7.0 mg/dL) at time of study drug administration

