- Screening baseline serum 25OH vitamin D of at least 13 ng/ml
- No medical contraindication to supplemental vitamin D for participants whose levels are >13 ng/ml but sub-therapeutic (<32ng/ml)
- No medical contraindication to supplemental calcium
- Weight under 300 pounds, which is the maximum permitted on the DXA scanner

Exclusion criteria:

- Ventilator dependent individuals who are not in weaning phase and are unable to provide consent through alternative communication
- Chronic steroid use (defined as >6 months)
- Rheumatoid disease with use of prior disease modifying anti-rheumatic drugs (DMARDs) affecting bone density
- History of osteoporosis or of treatment for osteopenia or osteoporosis with bisphosphonates, or selective reuptake estrogen modifying agents
- Current use of medications* including bisphosphonates to treat osteoporosis (*note that prior calcium or vitamin D use is not an exclusion criteria)
- History of more than one lower extremity osteoporosis-related fracture
- Chronic renal insufficiency, creatinine clearance < 35 ml/min, during screening
- End stage liver or kidney disease
- Medical conditions resulting in hypogonadal states that affect bone density
- Uncontrolled thyroid disease/thyroiditis
- Hereditary or acquired metabolic bone disorder
- History of use of unfractionated heparin for >1 year
- History of selected antiseizure medications, specifically phenobarbital, phenytoin, carbamazepine, sodium valproate >1 year
- Acute or chronic bilateral lower extremity fractures involving tibia or femur, with placement of surgical hardware in any areas of above locations
- Severe hypotension requiring use of IV blood pressure agents such as dopamine, norepinephrine, or phenylephrine. Exception may allow for patients on pressors who are experiencing hypotension as they acclimate to upright posture
- Inability to provide informed consent and understand the consent process
- Facial fractures requiring oral surgery

- Dental surgery or oral maxillofacial surgery within 2 weeks of anticipated study drug administration
- Pregnancy present on admission
- Vitamin D deficiency on admission testing (serum 25-OH D reported as < 13 ng/mL)
- Patients with an established reaction to, or history of, anaphylactic shock to aspirin

D.3. Methods

1. Sample Size Calculations

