A. Screening: Post injury days 0-17

- Subjects admitted to the RSCIC with suspected complete SCI will be approached for participation shortly after admission. After providing informed consent, subjects will be screened between 0 and 17 days post injury. The screening will review of the medical record medical/surgical history and physical/neurological examination performed according to ISNCSCI guidelines to ensure an AIS Grade A SCI is present, or post-menopausal) and social or lifestyle factors that could alter ability to participate.
- A serum pregnancy test (for females of child bearing age).
- Standard of Care laboratory tests of kidney (TJUH Basic Metabolic Panel) and liver function (TJUH Hepatic Panel) will be reviewed to ensure the patient does not have a history of chronic liver or kidney failure, unknown to family or subject or not revealed on subject history interview.

- Serum calcium measurement. If initial serum calcium is <7.0 mg/dl, the subject will be given correctional calcium doses in accordance with standard hospital treatment protocol for subjects with critically low calcium levels. The subject may still be able to participate if the calcium level is corrected by the day prior to study drug infusion.
- Serum Vitamin D measurement. Subjects with initial vitamin D levels in the deficient range (<13ng/ml) will not be eligible for participation. If subject's 25-OH vitamin D is between 13 and 20, the subject will be supplemented with high potency oral ergocalciferol 50,000 International Units (IU) per week until retesting occurs at 4 weeks. At the time the screening value is returned, subjects with 25-OH vitamin D levels between 20 and 32 will be started on 2000 IU vitamin D daily and those with levels 32 and higher will be initiated on 1000 IU daily. Supplemental oral calcium of 1200 mg daily will be started on the same day as the vitamin D, except in cases of low values as described above.
- Intact Parathyroid Hormone (iPTH) measurement.

B. Baseline Assessments: Post-injury days 8-21

A Baseline Assessment will be completed between 8 and 21 days post-injury, and include the following:

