Since serum 25OH vitamin D represents a storage level of vitamin D accumulated over the preceding months, subjects with therapeutic values immediately after injury may have normal vitamin D stores which decline in subsequent months. For this reason, vitamin D levels in all subjects will be monitored not only at baseline but also at months 1, 4, 8 and 12. Subjects will be supplemented with 50,000 IU oral ergocalciferol weekly, if insufficient (serum level 13-20 ng/ml); 2000 IU cholecalciferol or ergocalciferol daily, if sub-therapeutic (serum vitamin D level 21-31ng/ml). Those subjects in the therapeutic range for serum 25-OH vitamin D will be given a maintenance dose of 1000 IU oral vitamin D daily.

Table 4: Study Events and Visit Schedule

	Screening (Day 0-17)	Baseline (Day 8-21)	Study Drug and Acetaminophen Administration (within 21 days of injury)	1 month + / - 4 days	4 months + / - 7 days	8 months + / - 14 days	1 year + / - 14 days
Medical History Standard Care	X						
Physical Exam Standard Care	X						
Basic Metabolic and Hepatic Panel) Standard Care	X						
FRAX Score		X					
Study Drug Infusion			X				
Acetaminophen Administration			X ^a X ^b				
Serum calcium, magnesium, phos Standard Care	X	X		X	X	X	X
Serum 25OH-D Standard Care	X			X	X	X	X
Serum iPTH ^d Study Specific	X			X	X		X
P1NP ^e Study Specific		X		X	X		
IL-1 beta ^f Study Specific		X		X			
Serum CTX ^g Study Specific		X		X	X		X
CPK ^h Study Specific		X					
DXA** Study Specific		X ^c			X		X

- a) Administered every 4 hours for the first 24 hours following study drug infusion
- b) Administered every 4 hours PRN through day 3 following study drug infusion
- c) To be obtained as soon as medically stable to undergo DXA testing
- d) iPTH Blood Test Intact parathyroid hormone
- e) P1NP Blood Test N-terminal propeptide of Type I collagen
- f) IL-1 beta Blood Test Interleukin 1 beta
- g) S-CTX Blood Test Serum carboxy-terminal telopeptide of type I collagen
- h) CPK Blood Test Creatinine Phosphokinase

Table 5 Schedule of follow up contacts for **Years 2 through 4** of the study.

	Year 1 Every 2 Months	Year 2 Month 6	Year 2 Month 12	Year 3 Month 6	Year 3 Month 12	Year 4 Month 6	Year 4 Month 12
Questions about fractures	X	X	X	X	X	X	X
Questions about Vitamin D/calcium supplements	X	X	X	X	X	X	X
Questions about exercise and other treatments	X	X	X	X	X	X	X

Questions about functional status	X	X	X	X	X	X	X
-----------------------------------	---	---	---	---	---	---	---

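### The vitamin D contraindication check stops at 32 ng/ml, although every subject is given vitamin D (minor eligibility correction)

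*Combined protocol and SAP*

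**What the plan says.** The inclusion criteria in Section D.2 contain three related lines. The first sets the floor for entry: "Screening baseline serum 25OH vitamin D of at least 13 ng/ml". No upper limit is given. The second is the contraindication check at issue: "No medical contraindication to supplemental vitamin D for participants whose levels are >13 ng/ml but sub-therapeutic (<32ng/ml". The third, for calcium, has no restriction by level: "No medical contraindication to supplemental calcium".

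The supplementation rules are wider than the second line:

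- Section C, in the list of differences from earlier studies (item 3): "we will supply supplemental calcium and vitamin D to all subjects".
- Section D.3, item 4, part A (Screening): "those with levels 32 and higher will be initiated on 1000 IU daily".
- Section D.3, item 4, part J (vitamin D monitoring): "Those subjects in the therapeutic range for serum 25-OH vitamin D will be given a maintenance dose of 1000 IU oral vitamin D daily".

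Part J also explains why levels are repeated at months 1, 4, 8 and 12: "subjects with therapeutic values immediately after injury may have normal vitamin D stores which decline in subsequent months". A subject whose level falls into the sub-therapeutic band goes to 2000 IU daily, and one in the insufficient band to 50,000 IU of ergocalciferol weekly.

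**The concern.** An eligibility check on a supplement should cover the same people as the supplement. Here the check covers a middle band of screening levels, while dosing covers everyone who enters. A patient at or above 32 ng/ml with a contraindication specific to vitamin D meets the criteria as written, and the protocol then directs that vitamin D be started.

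Two features make the restriction look misplaced. Any patient whose 25-OH vitamin D is already too high is necessarily in the unchecked group, and Section D.2 says that earlier vitamin D use does not exclude. In addition, the protocol expects some subjects with good initial levels to decline, which would take them to the higher doses with no contraindication check stated at that step.

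What is at stake is a small safety and eligibility matter. Vitamin D is background supplementation in both arms, so the sample size, the analysis and the comparison of zoledronic acid with placebo do not depend on it.

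**Working it through.** The plan states no figure to reproduce. The main check sets the criterion against the dosing rules by screening level.

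| Screening 25-OH vitamin D | Eligible on level? | Contraindication check applies? | Starting vitamin D dose |
|---|---|---|---|
| Below 13 ng/ml | No | Not relevant | None in trial |
| Exactly 13 | Yes | No (criterion says above 13) | 50,000 IU weekly |
| Above 13, below 20 | Yes | Yes | 50,000 IU weekly |
| 20 to below 32 | Yes | Yes | 2000 IU daily |
| 32 or above | Yes | **No** | 1000 IU daily, more if the level falls |

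The 32-or-above row is the gap. The row for exactly 13 is a boundary slip affecting one laboratory value.

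**Other text that might close the gap.** The calcium criterion reaches contraindications shared with calcium. Section D.2 also excludes creatinine clearance below 35 ml/min, end stage liver or kidney disease, and metabolic bone disorders. None of these names vitamin D. The serum calcium criterion, "Serum calcium level >7.0 mg/dL", sets only a lower limit. No passage gives a vitamin D or calcium level at which vitamin D is withheld.

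**Share of eligible patients outside the check.** The inputs are Table 2 in Section C (acute SCI patients by season) and the planned enrolment of 48 from the sample size section. The assumption is that enrolment mirrors Table 2, which describes acute SCI patients in general and not this trial's eligible population.

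Share = (% at 32 or above) / (% at 13 or above)

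- Summer: 34.5 / (34.5 + 31.0 + 27.6) = 34.5 / 93.1 = 0.371; 48 × 0.371 = 17.8 subjects
- Winter: 15.4 / (15.4 + 30.8 + 23.0) = 15.4 / 69.2 = 0.223; 48 × 0.223 = 10.7 subjects

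So about 11 to 18 of 48 are unchecked. The ends correspond to all-winter and all-summer enrolment; four years of recruitment would mix seasons and land between them.

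**Illustration of the number affected.** The documents do not say how common a vitamin D contraindication missed by the other criteria would be. Taking p = 0.5% to 2% purely as an assumed range:

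- Expected number = n × p: 10.7 × 0.005 = 0.05, up to 17.8 × 0.02 = 0.36
- Chance of at least one = 1 − (1 − p)^n: 1 − 0.995^10.7 = 0.05, up to 1 − 0.98^17.8 = 0.30

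The upper figure pairs the all-summer extreme with the highest assumed prevalence. If the true prevalence is zero, both results are zero.

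**The case against.** The best defence is that the unchecked group may contain no one who matters. Every subject also starts 1200 mg of oral calcium daily alongside the vitamin D, and the calcium criterion applies at all levels. High serum calcium is an obvious reason to withhold a calcium supplement, so the missing upper limit on serum calcium adds little by itself. Screening includes a history review, metabolic and hepatic panels and intact parathyroid hormone. Serum calcium is measured at infusion, on days 1, 3, 7 and 14 afterwards, and at months 1, 4, 8 and 12. The documents name no condition that bars vitamin D but not calcium.

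Much of this stands: the safeguards overlap and the remaining group is small, possibly empty. It does not remove the mismatch, because none of these provisions is a check on vitamin D, and repeat testing comes after dosing has begun.

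A second defence is that the restriction was deliberate. The checked band matches the levels that get corrective doses at entry, while those at 32 or above get only the lowest dose. The protocol gives no such reason, and the reading fails on part J, which expects some therapeutic levels to fall and then assigns the corrective doses without a further check.

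The 5% to 30% chance above is also open to criticism as resting on an invented prevalence. That is fair if it is read as an estimate. It shows only what the assumed range would imply.

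**Conclusion.** The concern holds, as a minor one. The vitamin D contraindication criterion is narrower than the group that receives vitamin D, and a patient at 32 ng/ml or above with a contraindication specific to it is eligible as written. This follows from the text alone and does not depend on any assumption.

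The scale does depend on assumptions. About 11 to 18 of 48 subjects would be outside the check if enrolment resembles Table 2. The number with a contraindication that nothing else catches is unknown; it is well under one subject across the assumed 0.5% to 2% range and may be none. There is no effect on power, analysis or the treatment comparison. The correction is worth considering at the next amendment and is not a reason to delay the trial.

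**What to change.** In Section D.2, delete the part of the vitamin D contraindication line that limits it to levels above 13 and below 32 ng/ml. The line then requires the absence of a medical contraindication to the supplement at every eligible level, in parallel with the calcium line that follows it. The same deletion removes the mismatch at exactly 13 ng/ml.

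The cost is one clause in one inclusion criterion. It needs no extra test, visit or analysis. The only downside is that occasionally one more patient becomes ineligible, with an expected loss of 0.05 to 0.36 of 48 subjects under the assumed range.

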- Completion of the World Health Organization (WHO) Fracture Risk Assessment Tool (FRAX)⁷³. The FRAX asks for information about age, date of birth, sex, weight, height, previous fracture history, parental fracture history, smoking, steroid use, history of rheumatoid arthritis, presence of a medical condition related to osteoporosis, alcohol use, and current hip bone mineral density (see data collection forms in Appendix B). All data are then entered into the FRAX website (available through the WHO) to obtain the 10 year probability of a fracture. No personal identifiers are used and no data is saved on the website.
- Collection of blood sample for pre-treatment levels of PINP as measures of bone formation, s-CTX as marker of bone resorption, IL-1 β as a pro-osteoclastogenic factor, CPK (Creatinine Phosphokinase) as a marker of muscle tissue and kidney function, and serum calcium. DXA scan, to be obtained as soon as the subject is medically stable for testing off the intensive/acute care floor (may be done up to 7 days after the infusion of study drug).

C. Study drug infusion: Post injury day 21

Within day 21 post injury, subjects will be administered study drug and assessed as follows:

- Measurement of serum calcium level to ensure therapeutic levels.
- A single IV infusion of ZA 5 mg or a placebo drug with the same dilution and duration of administration (prepared and dispensed by the TJUH IDS).
- The single IV infusion will be administered over a 2 hour period (2.5 mg per hour)
- Supplemental hydration as needed to keep urine output > 2000 cc per day from the day prior to study drug administration until 3 days post-infusion.
- Acetaminophen 650 mg every 4 hours for the 24 hour period following drug administration. This is intended to reduce the frequency and severity of fever or myalgias associated with ZA administration⁶¹.

D. Days 1-7, Post Drug Infusion

- After the first day, acetaminophen will continue to be offered as needed every 4 hours through day 3 post-infusion.
- Supplemental hydration will be continued as needed to keep urine output > 2000 cc per day until 3 days post-infusion
- Subjects will be assessed daily for 3 days, then weekly for one month after study drug administration for known side effects of the drugs, including myalgias, fever, gastrointestinal disturbances, and flu-like symptoms.

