Information on Physical Examinations and Clinical Assessments

Objective Evaluations: To ensure the patient has a complete spinal cord injury (AIS Grade A), investigators will perform a complete neurological exam according to ISNCSCI guidelines as part of initial screening (days 2-17 post injury). A confirmatory exam will be conducted in the 24 hours prior to study drug delivery. At the end of the study when the patient returns for final laboratory tests and DXA scan, a repeat neurological examination will be performed.

Subjective reports: Interviews will be conducted with patients every 2 months during the first year, either in person if testing is scheduled, or by phone between testing sessions. The first phone call will occur 2 months from injury if the subject is not an inpatient or not available for in-person interview. During these interviews, subjects will be asked about any evidence or knowledge of bone fractures since the previous contact. We will obtain information about exercises and standing, (including use of FES), such as how often and average daily duration.

Follow up for Subsequent Years of Grant Cycle

During the subsequent years of the grant cycle, patients will be contacted every 6 months for information on fractures sustained in the prior 6 months. As part of the consent form, we will be requesting permission to receive x-ray reports of any bone fracture experienced and mechanism of injury between years 1 and 4 post injury and collect information on participation in standing, lower extremity exercise and functional electrical stimulation (FES), and current calcium and vitamin D use.

[figure not shown]
Early Termination

Should a subject gain neurological function prior to initial drug administration and no longer have a complete SCI, that potential subject is withdrawn from the study. Should a subject recover neurological function and the SCI be deemed incomplete any time after the study drug has been administered, that participant will continue with all assessments and follow up studies without exception.

5. DXA Scan Analyses

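### The pregnancy exclusion is checked by one serum test at screening (days 0-17) and not rechecked before dosing (up to day 21), so a very early pregnancy can go undetected

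*Combined protocol and SAP*

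**What the plan says.** The only pregnancy criterion is the exclusion in D.2, "Pregnancy present on admission". The only test is in D.3, item 4, A. Screening: "A serum pregnancy test (for females of child bearing age" and, on timing, "subjects will be screened between 0 and 17 days post injury". Patients "will be approached for participation shortly after admission", and the site description under Study Location and SCI Population states: "Over 50 percent of the SCI patient population is admitted to the RSCIC within three days of injury". A test in the first days after injury is therefore a realistic path.

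Dosing can come later. Item 4, C. Study drug infusion, opens: "Within day 21 post injury, subjects will be administered study drug and assessed as follows". The one laboratory check listed there is "Measurement of serum calcium level to ensure therapeutic levels". The section on physical examinations and clinical assessments adds a repeat neurological check: "A confirmatory exam will be conducted in the 24 hours prior to study drug delivery". Neither these places, nor the baseline list (days 8 to 21), nor Table 4 contains a second pregnancy test. Table 4 does not show the screening test either.

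**The concern.** An exclusion protects subjects only as far as it is verified. Here the verification may be done on the day of injury, and the infusion may follow up to three weeks later. A pregnancy too recent to show on the first test could become detectable in that interval, and nothing in the schedule would reveal it.

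At stake is the plan's evident intention that pregnant women should not receive study drug. The treatment is one infusion and cannot be withdrawn once given. With 2:1 allocation, a missed case would more likely than not receive active drug. The matter concerns eligibility and safety. It does not touch the sample size, the power or the type I error rate.

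**Working it through.** **Inputs from the documents.** Test day t lies between 0 and 17 (Screening). The latest dosing day is 21. The pre-treatment blood sample is drawn in the baseline window, days 8 to 21, so day 8 is the earliest infusion that the schedule implies.

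**Input assumed.** L is the number of days from conception to a positive serum test. The documents do not give it, so it is varied over 7, 10 and 14 days.

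**Step 1: interval from test to dose.** For infusion on day 21 the interval is 21 - t: 21 - 0 = 21 days at the longest and 21 - 17 = 4 days at the shortest. This describes the schedule. It is not the period at risk.

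**Step 2: the period at risk.** Take conception on or before the day of injury. A test on day t misses conceptions in the last max(0, L - t) days before injury.

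| Test day t | L = 7 | L = 10 | L = 14 |
|---|---|---|---|
| 0 | 7 | 10 | 14 |
| 3 | 4 | 7 | 11 |
| 7 | 0 | 3 | 7 |
| 10 | 0 | 0 | 4 |
| 14 | 0 | 0 | 0 |
| 17 | 0 | 0 | 0 |

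The last test day with any miss is L - 1, which is day 6, 9 or 13. The gap therefore belongs to the early part of the screening window, which is also when patients are likely to be approached.

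**Step 3: effect of a test tied to dosing.** A test on dosing day d misses max(0, L - d) days. For d = 21 this is 0 for all three values of L. For d = 8 it is 0, 2 or 6 days (8 exceeds 7; 10 - 8 = 2; 14 - 8 = 6). A repeat test never does worse than the earlier one, but with early dosing it narrows the gap without always closing it.

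**Step 4: how many subjects.** The documents give no expected share of women. If it were 15% to 25%, then 0.15 × 48 = 7.2 and 0.25 × 48 = 12, or about 7 to 12 women. Eligibility runs to age 65, so those of child-bearing age would be fewer. Those who were both tested early and conceived within days of injury would be a small fraction of these.

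**The case against.** The strongest objection is that the rule itself is sound. A reader might infer that the exclusion, being tied to admission, lets through a woman who conceived just before injury. It does not: that pregnancy exists on admission whether or not a test has found it. The wording omits only conception after admission, which is a remote possibility in newly injured inpatients with complete injury. This stands, and it places the weakness in the single early test.

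A second objection is that pregnancy is not the odd one out. Calcium and AIS grade are rechecked before dosing, but D.2 also ties creatinine clearance to screening and vitamin D deficiency to admission testing, and neither is listed for recheck before infusion. This also stands. The documents do not support a claim that every other changeable condition is tied to dosing; calcium and AIS grade serve only as precedents.

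Third, the documents may say more than can be seen. The screening sentence just before the pregnancy test is broken around a reference to menopausal status, and the consent pages were removed. Table 4 is not exhaustive: it also leaves out the infusion-day calcium and the confirmatory neurological examination, so its silence is weak evidence. These points lower the certainty, but none of the text available supplies a later check.

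Finally, the documents do not describe fetal risk from the drug. Congenital anomaly appears only as one item in the general definition of a serious adverse event under Safety Monitoring. The point therefore rests on the plan's own decision to exclude pregnancy, without any claim about the size of the harm.

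**Conclusion.** The point holds in a limited form. The exclusion is adequately worded for conception before injury, but its single test may fall too early to enforce it. A very early pregnancy could then be dosed without any departure from the written procedures.

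The size depends on the assumed detection lag. With 7 to 14 days, a day-0 test leaves 7 to 14 days of pre-injury conception uncovered, and a test from about day 7 to 14 onward leaves none. A reader might take the 4-to-21-day interval between test and dose as the period at risk, or suppose that the gap spans the whole screening window. Neither follows: a day-17 test has the 4-day interval and, under these lags, misses no pre-injury conception.

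The expected number of cases is very small. This is a low-frequency verification gap that is cheap to close. It gives no reason to doubt the trial's statistical design.

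**What to change.** Reconcile four places: the exclusion in D.2, the screening list, the infusion-day list (both in D.3, item 4) and Table 4. Together they should state when pregnancy status is verified relative to the dosing day, as the plan already does for calcium and AIS grade. One example is to run the serum test already specified, for females of child-bearing age, on the calcium sample taken for the infusion, with the result available before the drug is given. Table 4 should show each pregnancy test that the text requires. Stating the exclusion relative to dosing would also cover conception after admission.

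The cost is one extra assay for a handful of women on blood already being drawn, the wait for that result, and a few lines of text. Sample size and analysis do not change.
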